5.4. Number of subjects

Former study ZOSTER-041 subjects, who have a complete primary vaccination course (2 doses of HZ/su vaccine) will be offered enrollment into study ZOSTER-073 at participating centers.

Up to a maximum of 86 subjects will be targeted for enrollment. Assuming full enrollment and considering a 15% drop-out rate (including subjects not eligible in the per-protocol set), approximately 73 evaluable subjects are expected to complete the study.

Refer to Section 10.1 for further information on sample size determination.

CONFIDENTIAL212340 (ZOSTER-073 EXT:041 Y4-10)
Protocol Amendment 1 Final

Withdrawals will not be replaced.

Overview of the recruitment plan

The study will include subjects in multiple centers in countries that previously participated in study ZOSTER-041.

At the time of initiation of study ZOSTER-073, the investigator will contact ONLY those subjects who had a complete HZ/su vaccination course (2 doses of HZ/su vaccine) in study ZOSTER-041 and who expressed a willingness to participate at a potential follow-up study when questioned at the conclusion of the primary study. The reason for non-participation in study ZOSTER-073 will be documented in the site's screening log.

5.5. Subject and study completion

A subject is considered to have completed the study if he/she returns for the concluding visit (Visit 7; Month 49) as described in the protocol.

Global completion of the study is required in order to provide sufficient subjects as defined in Section [10.1](#) Sample Size Determination.

6. STUDY POPULATION

6.1. Inclusion criteria

Deviations from inclusion criteria are not allowed because they can potentially jeopardize the scientific integrity, regulatory acceptability of the study or subject safety. Therefore, adherence to the criteria as specified in the protocol is essential.

6.1.1. Inclusion criteria for enrollment (to be checked at Visit 1)

All subjects must satisfy ALL the following criteria at study entry:

- Subjects who, in the opinion of the investigator, can and will comply with the requirements of the protocol (e.g. completion of the diary cards, return for follow-up visits). Or/and subjects' Legally Acceptable Representative(s) [LAR(s)] who, in the opinion of the investigator, can and will comply, with the requirements of the protocol (e.g. completion of the diary cards, return for follow-up visits).
- Written informed consent obtained from the subject/LAR(s) of the subject prior to performance of any study-specific procedure.
- Subjects who previously participated in study ZOSTER-041 and completed the full 2 dose HZ/su primary vaccination course.

CONFIDENTIAL212340 (ZOSTER-073 EXT:041 Y4-10)
Protocol Amendment 1 Final**6.1.2. Inclusion criteria for revaccination (to be checked at Visit 3)**

All subjects must satisfy ALL enrollment criteria and the following criteria at revaccination Visit 3:

- Subjects receiving maintenance CIS therapy for the prevention of allograft rejection for a minimum of one month (30 days) prior to the first revaccination.
- Subjects without an episode of allograft rejection within 90 days prior to the first revaccination visit.
- Female subjects of non-childbearing potential may be revaccinated. Non-childbearing potential is defined as pre-menarche, current bilateral tubal ligation or occlusion, hysterectomy, bilateral ovariectomy or post-menopause.

Refer to [Glossary of terms](#) for definitions of menarche and menopause.

- Female subjects of childbearing potential may be revaccinated, if the subject:
 - has practiced adequate contraception for 30 days prior to revaccination, and
 - has a negative pregnancy test on the day of revaccination, and
 - has agreed to continue adequate contraception up to 2 months after completion of the revaccination series.

Refer to [Glossary of terms](#) for definitions of woman of child bearing potential and adequate contraception.

Note: Subjects not meeting the above inclusion criteria for revaccination may continue to participate in the study for long-term immunogenicity and safety evaluations at study Visits 6 and 7.

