12.5.12.3. Follow-up of pregnancies

Pregnant subjects will be followed to determine the outcome of the pregnancy. At the end of the pregnancy, whether full-term or premature, information on the status of the mother and child will be forwarded to GSK using the electronic pregnancy report and the Expedited Adverse Events Report if applicable. Generally, the follow-up period doesn't need to be longer than 6 to 8 weeks after the estimated date of delivery.

Regardless of the reporting period for SAEs for this study, if the pregnancy outcome is a SAE, it should always be reported as SAE.

CONFIDENTIAL212340 (ZOSTER-073 EXT:041 Y4-10)
Protocol Amendment 1 Final**12.6. Appendix 6: Contraceptive guidance and collection of pregnancy information****12.6.1. Definitions****12.6.1.1. Woman of Childbearing Potential (WOCBP)**

A woman is considered fertile following menarche and until becoming post-menopausal unless permanently sterile (see below)

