12.6.1.1.1. Women in the following categories are not considered WOCBP

- Premenarchal

Menarche is the onset of menses for the first time in a young female and is preceded by several changes associated with puberty including breast development and pubic hair growth. Menarche usually occurs within 1-2 years of breast development, thelarche. However, a young female can become pregnant before her first menses. Thus, a conservative definition of non- childbearing potential in a pre-menarcheal female is a young female who has not yet entered puberty as evidenced by lack of breast development (palpable glandular breast tissue).
- Premenopausal female with ONE of the following:
 - Documented hysterectomy
 - Documented bilateral salpingectomy
 - Documented bilateral oophorectomy

Note: Documentation can come from the site personnel's: review of subject's medical records, medical examination, or medical history interview.

- Postmenopausal female

A postmenopausal state is defined as no menses for 12 months without an alternative medical cause. A high follicle stimulating hormone (FSH) level in the postmenopausal range may be used to confirm a postmenopausal state in women not using hormonal contraception or hormonal replacement therapy (HRT). However, in the absence of 12 months of amenorrhea, a single FSH measurement is insufficient.

- Females on HRT and whose menopausal status is in doubt will be required to use 1 of the non-hormonal highly effective contraception methods if they wish to continue their HRT during the study. Otherwise, they must discontinue HRT to allow confirmation of postmenopausal status before study enrollment.

CONFIDENTIAL212340 (ZOSTER-073 EXT:041 Y4-10)
Protocol Amendment 1 Final**12.6.2. Contraception guidance**

Female subjects of childbearing potential are eligible to participate if they agree to use an adequate contraception consistently and correctly according to the methods listed in GSK list of highly effective contraceptive methods provided in [Table 25](#).

Table 25 Highly Effective Contraceptive Methods

Highly Effective Contraceptive Methods That Are User Dependent ^a Failure rate of <1% per year when used consistently and correctly.
Combined (estrogen- and progestogen-containing) hormonal contraception associated with inhibition of ovulation 
 • oral • intravaginal • transdermal

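### Protocol 6.1.2 and Appendix 6 classify a premenopausal woman with tubal ligation or occlusion in opposite ways, so she has either 0 or 2 scheduled pregnancy tests before revaccination

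*Protocol*

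**What the plan says.** **Section 6.1.2 (inclusion criteria for revaccination).** "Non-childbearing potential is defined as pre-menarche, current bilateral tubal ligation or occlusion, hysterectomy, bilateral ovariectomy or post-menopause". Women in these groups may be revaccinated without further conditions on fertility. A woman of childbearing potential must, among other conditions, meet this one: "has a negative pregnancy test on the day of revaccination". The section then refers to the Glossary "for definitions of woman of child bearing potential and adequate contraception".

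**Appendix 6.** Section 12.6.1.1 sets the default: "A woman is considered fertile following menarche and until becoming post-menopausal unless permanently sterile". Section 12.6.1.1.1 gives three exceptions for premenopausal women: hysterectomy, oophorectomy on both sides, and "Documented bilateral salpingectomy". Tubal ligation and tubal occlusion are not among them. Section 12.6.2 is addressed to women of childbearing potential and requires contraception "according to the methods listed in GSK list of highly effective contraceptive methods provided in" Table 25. That table includes bilateral tubal occlusion among the user-independent methods.

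**Testing and the bar on dosing.** The Schedule of Activities (Table 3), section 5.3 and section 8.1.7 limit the pregnancy test to females of childbearing potential, before vaccination at Visits 3 and 4. The bar is wider: sections 6.2.3 and 7.7 exclude any pregnant woman from dosing, whatever her class.

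**The concern.** The same woman falls into opposite classes in two parts of the current protocol, and no section says which part governs. The one cross-reference that should settle it fails. The Glossary in Appendix 1 begins at adverse event and ends at unsolicited adverse event. It has no entry for a woman of childbearing potential or for adequate contraception, and no redaction is visible where either term would fall alphabetically.

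The class decides whether a pregnancy is looked for before an adjuvanted vaccine is given. Under 6.1.2 the bar on dosing a pregnant woman still applies to a woman with tubal ligation or occlusion, but no test is scheduled that would reveal a pregnancy. Two sites could each follow the protocol and handle identical women differently.

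**Working it through.** The plan states no figure to reproduce. The check is a side-by-side reading and a count.

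| Premenopausal woman with | Section 6.1.2 | Appendix 6 |
|---|---|---|
| Hysterectomy | Not of childbearing potential | Not of childbearing potential |
| Both ovaries removed | Not of childbearing potential | Not of childbearing potential |
| Tubal ligation or occlusion, both sides | **Not of childbearing potential** | **Of childbearing potential** (not in the exceptions; occlusion is in Table 25 as contraception) |
| Both tubes removed (salpingectomy) | Not named | Not of childbearing potential |

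Inputs for the count:

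- Revaccination doses: 2, at Visits 3 and 4 (sections 7.1 and 7.4).
- Scheduled tests per dose: 1 if she is of childbearing potential, 0 if not (Table 3, sections 5.3 and 8.1.7).

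Formula: scheduled tests = (tests per dose) × (doses received).

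- Under 6.1.2: 0 × 2 = **0**.
- Under Appendix 6: 1 × 2 = **2**, one at Visit 3 and one at Visit 4.

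The count assumes that she is willing and receives both doses; section 8.1.7 drops the test for women unwilling to be revaccinated. Appendix 6 names occlusion and not ligation, but neither is in its list of exceptions, so the class is the same for both.

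**The case against.** The strongest reply is that this is an editorial mismatch with little practical weight. Pregnancy bars dosing under either definition. A physical examination at Visit 3 and a history-directed one at Visit 4 take place in any case (section 8.1.6), pregnancies are recorded throughout the study (section 8.1.13), and an investigator is free to test. The affected women are a subset of the 68 enrolled (SAP Table 1), who were aged 20 to 82 at first vaccination in ZOSTER-041. Their number may be zero. Choosing Appendix 6 over 6.1.2 is also a preference, since aligning either text to the other would end the conflict. All of this stands, and it limits the weight of the point. It does not remove the contradiction or supply the missing Glossary entry.

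A reader might infer more than the documents support:

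- **Loss from the per-protocol sets.** A woman dosed untested might seem open to SAP elimination code 2010 (revaccinated while ineligible). But the eligibility criterion carries its own definition of non-childbearing potential, and she meets it. To make her a violator, Appendix 6 would have to override that definition, and nothing in the SAP says it does.
- **Loss of eligibility.** Table 25 names occlusion but not ligation. Section 6.1.2 pairs the two, and on the natural reading ligation counts as a listed method, so she stays eligible under either definition.
- **A reverse conflict for salpingectomy.** This needs the 6.1.2 list to be read as closed. No text says so, and a woman whose tubes have been removed would naturally be treated as covered.
- **Missed contraception reminders.** These also follow the class, but a woman with tubal occlusion already uses a listed method, so a reminder changes nothing.
- **A second failed pointer.** Section 6.1.2 also sends the reader to the Glossary "for definitions of menarche and menopause". Redacted entries fall at that place in the alphabet, so absence cannot be shown. Appendix 6 covers both terms in any case; for example, "A postmenopausal state is defined as no menses for 12 months without an alternative medical cause".

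**Conclusion.** The contradiction is real and lies in current text. For a premenopausal woman with bilateral tubal ligation or occlusion who receives both doses, scheduled pre-dose pregnancy tests are 0 under 6.1.2 and 2 under Appendix 6. The pointer from 6.1.2 to the Glossary for childbearing potential and adequate contraception does not resolve it.

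This is a minor safety-wording point. The documents do not give the number of affected women or any probability of harm. Eligibility on the natural reading, the endpoints, the analysis sets and the sample size are not shown to change.

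**What to change.** Use one definition. Appendix 6 is the more cautious choice: its standard is permanent sterility, while 6.1.2 itself speaks only of a current ligation or occlusion.

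1. In 6.1.2, delete tubal ligation and occlusion from the non-childbearing list and add bilateral salpingectomy, to match Appendix 6.
2. In 6.1.2, redirect the pointer for woman of childbearing potential and adequate contraception from the Glossary to Appendix 6 (12.6.1, 12.6.2 and Table 25).
3. In Table 25, name bilateral tubal ligation beside occlusion, so that these women plainly have a listed method, stay eligible, and are tested before each dose.

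The cost is the wording edits plus two urine tests per affected woman. Both tests are already in the Schedule of Activities. The edits can help only women who have not yet been revaccinated.

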6.2. Exclusion criteria

Deviations from exclusion criteria are not allowed because they can potentially jeopardize the scientific integrity, regulatory acceptability of the study or subject safety. Therefore, adherence to the criteria as specified in the protocol is essential.

6.2.1. Exclusion criteria for enrollment (to be checked at Visit 1)

The following criteria should be checked at the time of study entry. If ANY exclusion criterion applies, the subject must not be included in the study.

6.2.1.1. Medical conditions

- Vaccination against HZ since completion of study ZOSTER-041.
- Significant underlying illness that, in the opinion of the investigator, is expected to prevent completion of the study.
- Any other condition that, in the opinion of the investigator, would interfere with the evaluations required by the study.

CONFIDENTIAL212340 (ZOSTER-073 EXT:041 Y4-10)
Protocol Amendment 1 Final**6.2.1.2. Prior/Concurrent clinical study experience**

- Concurrently participating in another interventional vaccine or immunosuppressive clinical study, in which the subject *is* exposed to an investigational or a non-investigational vaccine/product* (drug) *at any time during the ZOSTER-073 study.* **(Amended: 15 June 2020)**

*Allowed products: Immunosuppressant(s), which are investigational or non-registered product(s) at the local/country level, may be used if they are specifically prescribed for the prevention of allograft rejection and are:

- available locally through compassionate use programs,
- submitted for and pending local/country registration,
- approved and registered for use in one or more of the other participating countries with well-documented Summary of Product Characteristics (SPC) or Prescribing Information (PI).

The name of the active component(s) of these immunosuppressants must be provided in the concomitant medication listing.

6.2.2. Exclusion criteria for revaccination (to be checked at Visit 3)

All enrollment exclusion criteria and the following criteria should be checked at Visit 3. If ANY exclusion criterion applies, the subject must not be revaccinated.

6.2.2.1. Medical conditions

- History of confirmed HZ within one year before revaccination visit (Visit 3), i.e. HZ between Visit 2 (Month 12) and Visit 3 (Month 24).
- More than one organ transplanted (i.e. kidney-liver, double kidney, or kidney plus another organ(s) transplanted).
- Any additional confirmed or suspected immunosuppressive or immunodeficient condition (e.g., malignancy, HIV infection, systemic infection).
- History of any reaction or hypersensitivity (e.g. anaphylaxis) likely to be exacerbated by any component of the vaccine.
- Any other condition that, in the opinion of the investigator, would interfere with the evaluations required by the study or make vaccination unsafe.

6.2.2.2. Prior/Concomitant therapy

- Administration or planned administration of immunoglobulins and/or any blood products or plasma derivatives during the period starting 3 months (90 days) before the first revaccination dose of study vaccine and ending at Visit 5 (Month 26).

CONFIDENTIAL

212340 (ZOSTER-073 EXT:041 Y4-10)
Protocol Amendment 1 Final

- Use of anti-CD20 or other B-cell monoclonal antibody agents (e.g., rituximab, ocrelizumab) as maintenance and/or therapeutic immunosuppressive therapy for the prevention of allograft rejection within 9 months (274 days) of first revaccination dose of study vaccine.
- Evidence or high suspicion, in the opinion of the investigator, of noncompliance or nonadherence to use of maintenance immunosuppressive therapies.
- Planned administration/administration of a live vaccine in the period starting 30 days before the first dose and ending 30 days after the last dose of study vaccine administration.
- Planned administration/administration of a non-replicating or subunit vaccine,* not foreseen by the study protocol, in the period starting 8 days before and ending 30 days after each dose of study vaccine.

*E.g. inactivated and subunit vaccines, including inactivated and subunit influenza vaccines and pneumococcal conjugate vaccines.

6.2.3. Other exclusion criteria for revaccination

- Pregnant or lactating female.
- Female planning to become pregnant or planning to discontinue contraceptive precautions up to 2 months post-revaccination Dose 2.
- Any condition which, in the judgment of the investigator, would make intramuscular (IM) injection unsafe.

If any of the above exclusion criteria are met, the subject should be encouraged to remain in the study withdrawing only from revaccination, while continuing other study procedures (see section [8.4.5](#)). Alternatively, at the discretion of the investigator, the subject may be withdrawn from the study (see section [12.5.12](#)).

6.3. Criteria for temporary delay for revaccination

Revaccination may be postponed within the allowed time interval (see [Table 4](#)) until transient circumstances cited below have been resolved:

- Acute disease and/or fever at the time of revaccination. Fever is defined as temperature $\geq 38.0^{\circ}\text{C}$. The preferred route for measuring temperature in this study is oral. Subjects with a minor illness (such as mild diarrhea, mild upper respiratory infection) without fever may, be revaccinated at the discretion of the investigator.
- Allograft instability [greater than 20% variability between last two clinically obtained creatinine measurements or calculated glomerular Filtration Rates (GFR)].
- Any condition which, in the judgment of the investigator, would make IM injection unsafe.

CONFIDENTIAL212340 (ZOSTER-073 EXT:041 Y4-10)
Protocol Amendment 1 Final

7. TREATMENTS

Study treatment is defined as a set of investigational product(s) or marketed product(s) or placebo intended to be administered to a subject.

7.1. Treatments administered

All *eligible and willing* subjects will receive HZ/su vaccine (for details see [Table 7](#)).
(Amended: 15 June 2020)

Table 7 Treatments administered

Study Treatment Name:	HZ/su
Vaccine name	VZV gE AS01B
Presentation	Lyophilized pellet in a monodose vial Liquid in a monodose vial
Vaccine formulation:	gE=50µg MPL=50µg; QS21=50µg; Liposomes *
Route of Administration	IM injection
Administration site:	
Location	Deltoid
Laterality **	Non-dominant
Number of doses to be administered:	2
Volume to be administered ***	0.5 ml
Packaging and Labelling	Refer to SPM for more details
Manufacturer	GSK

*QS-21: *Quillaja saponaria Molina*, fraction 21 (Licensed by GSK from Antigenics Inc, a wholly owned subsidiary of Agenus Inc., a Delaware, USA corporation).

** The non-dominant arm is the preferred site of injection. In case it is not possible to administer the vaccine in the non-dominant arm, an injection in the dominant arm may be performed.

*** Refer to the SPM for the volume after reconstitution.

Refer to the Study Procedures Manual (SPM) for detailed instructions on study vaccine reconstitution.

After completing all prerequisite procedures prior to the first revaccination (including the review of inclusion and exclusion criteria [see sections [6.1](#) and [6.2](#), respectively]), one dose of study vaccine will be administered intramuscularly in the deltoid of preferably the non-dominant arm at Visit 3 (Month 24) (refer to [Table 7](#) for details regarding the treatment administered).

After completing all prerequisite procedures prior to the second revaccination (see section [7.7](#) regarding the contraindications to subsequent vaccination), one dose of study vaccine will be administered intramuscularly in the deltoid of preferably the non-dominant arm at Visit 4 (Month 25) (see [Table 7](#) for details regarding the treatment administered).

If the investigator or delegate determines that the subject's health on the day of administration temporarily precludes vaccine administration, the visit will be rescheduled within the allowed interval for this visit (refer to [Table 4](#)).

CONFIDENTIAL212340 (ZOSTER-073 EXT:041 Y4-10)
Protocol Amendment 1 Final

The subjects will be observed closely for at least 30 minutes following the administration of the vaccine, with appropriate medical treatment readily available in case of anaphylaxis and syncope.

7.2. Method of treatment assignment

7.2.1. Subject identification

Subjects will receive the same subject identification numbers as in primary study ZOSTER-041.

7.2.2. Randomization of treatment

This is a single arm, open-label, non-randomized study.

7.2.2.1. Treatment Allocation to the Subject

The number of each administered treatment assigned by Source data Base for Internet Randomisation (SBIR) must be recorded in the eCRF on the Vaccine Administration screen.

7.2.3. Allocation of subjects to CMI sub-cohort

At participating centers, that have access to Peripheral Blood Mononuclear Cell (PBMC) processing facility, up to a maximum of 40 subjects will be targeted for CMI collection such that approximately 34 evaluable subjects are available for CMI analyses, considering a 15% drop-out rate (including subjects not eligible in the per-protocol set).

The CMI analyses will be performed at specified timepoints for subjects included in the CMI-sub-cohort. CMI subjects from ZOSTER-041 (n = 28) will be targeted for enrollment into the ZOSTER-073 CMI sub-cohort. The balance of CMI subjects to be enrolled will be selected at random from CMI participating centers to complete the sub-cohort up to 40 subjects at Visit 1.

